## 9.2 SECONDARY EFFICACY VARIABLES

### 9.2.1 FOR FORMAL TESTING USING THE SEQUENTIAL APPROACH

If a significant beneficial Starling SV effect is found in the primary endpoint, the following secondary endpoints will be compared between treatments in the sequential manner discussed above.

#### 9.2.1.1 Changes in Serum Creatinine Levels from Baseline to 72 hours or ICU discharge

The hypotheses of interest relating to the mean change in serum creatinine level from baseline to 72 hours or ICU discharge, whichever comes first, are as follows:

$$H_0: \mu_t = \mu_c$$

$$H_1: \mu_t \neq \mu_c$$

where  $\mu_t$  and  $\mu_c$  represent the mean change in serum creatinine level from baseline to 72 hours in the treatment and control groups, respectively. The treatment groups will be compared with respect to the mean days using an analysis of covariance adjusting for baseline serum creatinine. Subjects that enter the study on dialysis are excluded from this endpoint. Subjects that are put on dialysis within 72 hours, or prior to ICU discharge, will have the final creatinine value prior to dialysis used for the change from baseline calculation. All creatinine values post dialysis treatment are not applicable to this endpoint test. Summary of this endpoint will include the mean, median, quartiles, minimum, maximum and standard deviation of levels for each treatment arm, a 95% confidence interval for the difference in the two treatment arm mean levels, and the p-value from the test described above.

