9. STUDY PROCEDURES

9.1 Baseline Assessments

After written informed consent is obtained, baseline assessments will be made to further determine the subject's eligibility for the study. Data collected will include:

- Demographics
- Age
- Medical history

- SOFA assessment
- Physical exam, limited
- Hemoglobin and blood gas (per chart review, if available)
- Serum creatinine level
- Lactate level (per chart review, if available)
- Urine sample (to be frozen for possible future testing)
- Optional plasma serum collection (two, 5ml samples to be frozen for possible future testing)
- Current medications

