9.3.3 Additional Data Collection

Other data points and associated times will be collected in addition to the analysis of the continuous data from the Starling SV system. Types of data points for collection are:

- Medical history
- Medications
- Volume of treatment fluid administered
- Urine output (to be recorded every 12 hours)
- Respiratory status
- Serum Creatinine level (every 24 hours +/- 4 hours , for 72 hour monitoring period and at 30 day discharge)
- Lactate level (per chart review, if available)
- Significant clinical events not previously identified for study data collection, e.g. cardiac arrest, CPR, intubation, extubation, placement of catheters (intravenous, arterial, urinary, etc), etc.
- Changes in mechanical ventilator status parameters

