### 7.5 MULTIPLE COMPARISONS AND MULTIPLICITY

It is recognized that with a multiplicity of tests comes inflation in the chance of a false finding. Therefore, formal statistical testing will only be done for the following secondary endpoints:

- Changes in serum creatinine level from baseline to 72 hours (key secondary endpoint)
- Requirement for renal replacement therapy (RRT)
- Requirement for ventilator use
- Length of ICU stay (days) until subject is medically ready for discharge
- Number of hours with ventilator use (30-day period)
- Number of hours with vasopressor use

These endpoints will be tested in a hierarchical (sequential) manner in the order given above (and testing will only proceed if a significant beneficial treatment effect is detected in the primary endpoint). Specifically, the first secondary endpoint (change in creatinine) will be compared between treatments at a two-sided 0.05 level of significance. If significant in the direction favoring Starling SV, then Starling SV will be considered beneficial on change in serum creatinine level, and the next endpoint (ICU stay) will be compared between treatments at a two-sided 0.05 level of significance; otherwise the statistical testing will stop and Starling SV will not be considered statistically significantly beneficial on any secondary endpoint. If the treatment comparison is able to proceed to this next secondary endpoint of ICU stay, it will be carried out at the two-sided 0.05 level of significance. If the treatment comparison is significant in the direction favoring Starling SV, then Starling SV will be considered beneficial on this endpoint and testing will proceed in a similar manner for the remaining endpoints; otherwise, treatment comparisons will stop and Starling SV will not be considered beneficial on this second secondary endpoint of ICU stay nor on all endpoints after it in the above sequence.

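### Scoring dialysed patients on their last pre-dialysis creatinine cuts the rise most for the earliest renal failures, and no planned analysis tests whether the creatinine result depends on it

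*SAP*

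**What the plan says.** SAP 9.2.1.1 compares mean change in serum creatinine from baseline to 72 hours or ICU discharge, whichever is first, by ANCOVA on baseline creatinine. Patients already on dialysis at entry are left out: "Subjects that enter the study on dialysis are excluded from this endpoint". Patients who start dialysis during the study stay in, under this rule: "Subjects that are put on dialysis within 72 hours, or prior to ICU discharge, will have the final creatinine value prior to dialysis used". Later values are discarded: "All creatinine values post dialysis treatment are not applicable to this endpoint test".

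Protocol 9.1 collects creatinine at baseline. Protocol 9.3.3 then schedules it as "Serum Creatinine level (every 24 hours +/- 4 hours , for 72 hour monitoring period and at 30 day discharge".

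The endpoint carries weight. SAP 5 derives the minimum of 120 patients from it. SAP 3.1.1 computes conditional power from it at 90 patients and may raise enrolment to as many as 210. SAP 7.5 tests it first among the secondaries, once the primary endpoint has succeeded. If it is not significant in Starling's favour, "otherwise the statistical testing will stop".

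RRT is a separate endpoint in SAP 9.2.1.2. The imputation-based sensitivity analysis in SAP 7.3 covers the primary endpoint only.

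**The concern.** The need for dialysis is itself a bad renal outcome, but in this endpoint it stops the clock. The sooner the kidneys fail, the less of the creatinine rise is counted. A patient dialysed on the first day can be scored as unchanged, and so rank better than a patient whose creatinine rose modestly to 72 hours without dialysis.

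The truncation depends on an outcome that treatment is hypothesised to affect. If guided care prevents dialysis, the rises cut short are mainly in the control arm, which weakens the test that must succeed before later secondaries can be claimed. If guided care leads to more dialysis, the cut rises are mainly on Starling and its mean change looks better than it is. A substituted value counts as observed, so nothing in the missing-data plan would flag it. Adjusting for baseline does not help, because the lost information is post-baseline.

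**Working it through.** **1. The plan's own figure.** Inputs from SAP 5: effect 1.4 mg/dL, SD 2.5 mg/dL, 80 and 40 patients, two-sided alpha 0.05.

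- SE = 2.5 × √(1/80 + 1/40) = 0.484
- Noncentrality = 1.4 / 0.484 = 2.89, with 118 df
- Two-sample t-test power = 81.8%

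The stated 80% is reproduced if read as at least 80%. The same method with 2 L and SD 3 L gives 92.7%, matching the primary endpoint figure in SAP 5.

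**2. Which value the rule picks, on scheduled draws only.**

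| Dialysis starts | Last scheduled value before it | Change scored |
|---|---|---|
| Before the first draw (hour 20-28) | Baseline | 0 |
| Hour 40 | About 24 h | Rise to about 24 h |
| Hour 60 | About 48 h | Rise to about 48 h |
| Not started | 72 h | Rise to 72 h |

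An unscheduled pre-dialysis result, if recorded, would replace these. If starts were spread evenly over 72 hours (assumption), the share scoring exactly zero would be 20/72 = 28% to 28/72 = 39%. With a linear rise, the average share of the 72-hour rise captured would be (0 + 24 + 48) / (3 × 72) = one third.

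**3. Effect on the between-arm difference.** Let p be the proportion starting RRT by the endpoint time and L the rise lost per dialysed patient.

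Benefit lost = (p_control − p_Starling) × L

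The documents give neither p nor L, so the rows below are assumptions. They also assume that 1.4 mg/dL is the untruncated effect, which SAP 5 does not say.

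Cutting large rises also reduces the variance, so power is shown two ways: with SD fixed at 2.5, and with each arm's variance reduced to 2.5² − p(1 − p)[D² − (D − L)²]. Here D is how far dialysed patients would otherwise lie above the rest at 72 hours, taken as 3-4 mg/dL.

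| RRT, control vs Starling | L (mg/dL) | Benefit lost | Remaining | Power, SD 2.5 | Power, reduced SD |
|---|---|---|---|---|---|
| 10% vs 5% | 1 | 0.05 | 1.35 | 79.0% | 81-82% |
| 10% vs 5% | 2 | 0.10 | 1.30 | 75.9% | 79-81% |
| 15% vs 5% | 2 | 0.20 | 1.20 | 69.1% | 73-76% |
| 20% vs 5% | 3 | 0.45 | 0.95 | 49.5% | 55-59% |

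Worked example for the third row with D = 3:

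- Control variance = 6.25 − 0.1275 × (9 − 1) = 5.23
- Starling variance = 6.25 − 0.0475 × (9 − 1) = 5.87
- Pooled SD = √[(79 × 5.87 + 39 × 5.23)/118] = 2.38
- Noncentrality = 1.20 / (2.38 × 0.1936) = 2.60, power 73%

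With equal rates and equal L, the benefit lost is 0.

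**4. The reverse direction.** Take RRT of 10% on Starling and 5% in control, with L = 3. Then (0.05 − 0.10) × 3 = −0.15, a spurious 0.15 mg/dL in Starling's favour. If the untruncated means were equal (SD 2.5), the noncentrality is 0.15/0.484 = 0.31. The chance of a significant result favouring Starling rises from 2.5% to 4.9%.

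All of these are t-test figures. The planned ANCOVA gains power if baseline creatinine is correlated with the change.

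**The case against.** Much of the case for the rule is sound. Dialysis lowers creatinine, so discarding post-dialysis values is right, and the rule keeps incident-dialysis patients in the analysis instead of dropping them. In the direction the sponsor hopes for, the bias works against the claim and so costs power, not validity. The SAP refers to the final value before dialysis, not the final scheduled one, so a zero is possible but not certain.

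Three stronger readings are tempting, and the documents do not support them.

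- **That a dialysis harm would be hidden.** SAP 9.2.1.2 requires the number and percentage needing RRT and a 95% confidence interval for the difference. The hierarchy in SAP 7.5 stops claims, not summaries. Protocol 10.1 also collects renal serious adverse events.
- **That a valid 72-hour value will be replaced when dialysis starts on, say, day 5 in the ICU.** The substitution sentence can be read so. But the opening of SAP 9.2.1.1 sets the endpoint at whichever of 72 hours and ICU discharge is first, and the sentence may only be repeating that window. The wording is ambiguous; it is not a demonstrated error.
- **That a particular power loss is established.** Every such figure rests on assumed RRT rates, and holding the SD fixed overstates the loss.

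What survives is that the separate RRT summary does not tell a reader whether the creatinine result depends on the truncation. Formal RRT testing also comes only after creatinine has succeeded. (The list in SAP 7.5 puts RRT second, while its text names ICU stay as next; that needs reconciling separately.)

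**Conclusion.** The point holds. The rule makes truncation depend on a renal outcome that treatment may change, in an endpoint that determines the sample size, the re-estimation and access to every later secondary claim. The mechanism follows directly from the rule and the sampling schedule.

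The size cannot be fixed from the documents. Under the assumptions shown, the distortion runs from nil with equal rates and timing, through 0.05-0.20 mg/dL, to 0.45 mg/dL. Power therefore ranges from essentially unchanged to between one half and three fifths. The direction depends on which arm has more RRT. The primary endpoint is unaffected.

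The defect is the absence of any analysis that counts dialysis as a bad renal outcome alongside the creatinine change, together with loose wording of the window. It should be corrected in the SAP; it is not a reason to abandon the planned test.

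**What to change.** - Keep the ANCOVA in SAP 9.2.1.1 as the formal test.
- Add one pre-specified sensitivity analysis. Patients starting RRT by the endpoint time (72 hours or ICU discharge, whichever is first) take the worst rank. All others are ranked by creatinine change, with adjustment for baseline creatinine. State how deaths before the endpoint time are ranked, since 9.2.1.1 has no rule for them.
- Report it beside the ANCOVA and interpret any creatinine benefit in its light. Do not make agreement a formal condition: that would change the claim rule and would not restore power.
- Reword the substitution so that it applies only to dialysis started before the endpoint time, so a valid 72-hour value is never replaced.
- Report by arm how many values were substituted and the hour of each.

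The cost is SAP wording and one further analysis on data already collected. Its result is on a rank scale, not in mg/dL. It shows whether the creatinine finding is robust, but it does not recover power in the formal test or change the input to the re-estimation.

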## 5 SAMPLE SIZE

Subjects will be randomly assigned in a 2:1 ratio to treatment with Starling SV or to treatment with standard of care, stratified by time window of enrollment (0-6 hours, 6-12 hours, and 12-24 hours). The primary effectiveness endpoint for this study is fluid balance at ICU discharge.

Minimum enrollment ( $N_{\min}$ ) in the study will be set at 120 subjects (80 Starling SV and 40 control) to power at 80% for demonstration of superiority of means for the secondary endpoint of creatinine levels as a measurement of change from baseline at 72 hours. The secondary endpoint for change in creatinine levels at 120 evaluable subjects displays 80% power at a two-sided alpha level of 0.05 to demonstrate superiority of Starling SV under an assumption of an average treatment effect of -1.4 mg/dL with a standard deviation of 2.5 mg/dL.

Under an assumption of an average treatment effect of -2 L with a standard deviation of 3 L, the sample size of 120 evaluable subjects provides 92.7% power in a test of superiority of means for the primary effectiveness endpoint at a two-sided 0.05 level of significance.

The trial will incorporate a sample size re-estimation (SSR) at the time of the interim look (after 90 patients have been evaluated for the key secondary endpoint) based on promise for superiority in the key secondary endpoint. Sample size re-estimation, described in further detail in Section 3.1, will result in a maximum of 210 total evaluable subjects, or no more than 1.75 times the minimum of 120.

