### 9.2.1.4 Length of ICU Stay

The distribution of treatments with respect to length of ICU stay (days) will be compared between treatments using the Wilcoxon Rank Sum test given the expected skewness in this variable. Subjects that die while in the ICU will be censored from the analysis. ICU length of stay will be calculated using the earliest of date that the subject is medically ready for discharge when captured, the date of discharge, or the study exit date.

Summary of this endpoint will include the mean, median, quartiles, minimum, maximum and standard deviation of days for each treatment arm, a 95% confidence interval for the difference in the two treatment arm mean days, and the p-value from Wilcoxon Rank Sum test.

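### For two formally tested secondary endpoints, ICU stay explicitly and creatinine change on a plain reading, the SAP reports a confidence interval that does not belong to the planned test

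*SAP*

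**What the plan says.** **Creatinine (SAP 9.2.1.1).** The hypotheses concern mean change from baseline. The arms are compared "using an analysis of covariance adjusting for baseline serum creatinine". The summary then gives "a 95% confidence interval for the difference in the two treatment arm mean levels, and the p-value from the test described above". The interval is not described as adjusted, least-squares or model-based, and it refers to levels. The sentence that names the test also speaks of mean days, which cannot apply to creatinine.

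**ICU stay (SAP 9.2.1.4).** Length of stay "will be compared between treatments using the Wilcoxon Rank Sum test given the expected skewness in this variable". The summary gives "a 95% confidence interval for the difference in the two treatment arm mean days, and the p-value from Wilcoxon Rank Sum test".

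**Standing of the two endpoints.** SAP 9.2.1 says that after a positive primary result "the following secondary endpoints will be compared between treatments in the sequential manner discussed above", and both endpoints are on that list. Creatinine comes first: under SAP 7.5 "the first secondary endpoint (change in creatinine) will be compared between treatments at a two-sided 0.05 level of significance". It also sets the minimum sample size in SAP 5.

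**Practice elsewhere in the SAP.** Sections 9.1, 9.2.1.5 and 9.2.1.6 pair a t-test with an interval for a difference in means. Sections 9.2.1.2 and 9.2.1.3 change the interval method when the test changes from chi-square to Fisher's exact.

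**The concern.** A reader expects a 95% interval printed beside a two-sided 0.05 test to exclude zero exactly when the test is significant. That holds only if both come from the same model and address the same contrast.

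For ICU stay they do not. The rank test compares distributions, while the interval compares means. The SAP moves away from means for the test because it expects skewness, then returns to them for the estimate.

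For creatinine, an unadjusted interval gives up the precision that the ANCOVA gains. If *levels* is taken literally, the interval is not even for the quantity in the hypotheses.

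What is at stake is the reported effect size and its consistency with the claim. This matters most for creatinine, which drives the sample size and heads the sequence.

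**Working it through.** **Inputs from the SAP.** Section 5: enrolment "will be set at 120 subjects (80 Starling SV and 40 control"); creatinine assumption "an average treatment effect of -1.4 mg/dL with a standard deviation of 2.5 mg/dL". Section 7.5: two-sided 0.05. The documents give no baseline-change correlation and no distribution for ICU stay, so both are assumed below and shown as ranges.

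**1. The plan's own figures.** The unadjusted standard error is 2.5 × √(1/80 + 1/40) = 2.5 × 0.1936 = 0.484 mg/dL, so the noncentrality is 1.4/0.484 = 2.89. Two-sample t power is 81.8%, against 80% stated. For the primary endpoint (-2 L, SD 3 L), 2/(3 × 0.1936) = 3.44 gives 92.7%, as stated. The inputs are therefore read as the plan intends.

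**2. Creatinine: width.** With baseline-change correlation r, the ANCOVA residual SD is 2.5 × √(1 - r²), so an unadjusted interval is wider by about 1/√(1 - r²):
- r = 0: 1.00, no excess width
- r = -0.3: 1/√0.91 = 1.05, 5% wider
- r = -0.5: 1/√0.75 = 1.15, 15% wider
- r = -0.7: 1/√0.51 = 1.40, 40% wider

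As an illustration at r = -0.5, the half-widths are 1.98 × 0.484 = 0.96 unadjusted and 0.96 × √0.75 = 0.83 adjusted. If both estimates came out at -0.9 mg/dL, the unadjusted interval would be -1.86 to 0.06 and the adjusted one -1.73 to -0.07. The significant ANCOVA would stand beside an interval that includes zero.

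**3. Creatinine: disagreement.** Simulation at 80:40, SD 2.5, 40,000 trials per case: ANCOVA p-value against the unadjusted pooled-t 95% interval for the difference in mean change. Entries are percent of trials.

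| True effect | r = 0 | r = -0.3 | r = -0.5 | r = -0.7 |
|---|---|---|---|---|
| -1.4: any disagreement | 1.8 | 6.5 | 11.7 | 16.7 |
| -1.4: test significant, interval includes 0 | 0.7 | 4.8 | 10.6 | 16.4 |
| -1.4: the reverse | 1.0 | 1.7 | 1.1 | 0.3 |
| -1.0: any disagreement | 2.3 | 10.2 | 18.8 | 32.6 |
| 0: any disagreement | 0.7 | 2.8 | 4.7 | 6.6 |

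At the planned effect, once r differs from 0, most disagreements are a significant test beside an interval that includes zero.

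**4. ICU stay: disagreement.** Simulation at 80:40, lognormal stay, 6,000 trials per case: Wilcoxon p-value against the pooled-t 95% interval for the difference in means. Entries are percent disagreeing, with the part that is a significant test beside an interval including zero in brackets.

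| Ratio of medians | log-SD 0.6 | log-SD 0.8 | log-SD 1.0 |
|---|---|---|---|
| 1 (no effect) | 3.8 (2.0) | 4.9 (2.7) | 5.4 (3.0) |
| 0.8 | 16.2 (8.9) | 16.4 (9.5) | 15.6 (8.9) |
| 0.7 | 10.7 (7.2) | 20.5 (13.5) | 22.7 (15.0) |
| 0.6 | 1.9 (1.2) | 12.3 (9.6) | 23.5 (17.5) |

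The SAP does not say whether the variance is pooled. With a Welch interval at log-SD 0.9, disagreement is 14.4%, 23.0% and 23.0% at ratios 0.8, 0.7 and 0.6, of which 12.3, 20.7 and 21.6 points are a significant test beside an interval including zero. At log-SD 1.0 the Welch figure reaches about 30%.

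**5. After the change.** The interval for the ANCOVA treatment coefficient excludes zero exactly when the ANCOVA p-value is below 0.05, so disagreement is nil by construction. The interval that inverts the rank test agrees with the Wilcoxon p-value apart from small effects of ties in whole days. N = 120 and the 0.05 level do not change.

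**The case against.** **The creatinine mismatch is an inference.** This stands in part. SAP 9.2.1.1 names no method for the interval, and the stray mention of mean days shows carry-over wording, so *levels* may be a slip as well. If least-squares means were intended, the interval would match. The SAP does not say so, and the plain reading is raw arm means. The needed edit is the same either way.

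**An unadjusted interval would still be valid.** This stands. Under randomisation the unadjusted and adjusted differences in mean change estimate the same quantity. The loss is precision and agreement with the test. A reader might infer bias, and the documents do not support that.

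**A reader might infer that the testing sequence or type I error is compromised.** It is not. SAP 7.5 decides each step by the two-sided test and the direction of effect; the intervals belong to the endpoint summaries. Direction is hardly at risk either: in the ICU-stay simulations, a significant rank test with a mean difference of opposite sign occurred in at most 0.2% of trials. ICU stay is also tested formally only if the primary endpoint and the secondary endpoints ahead of it succeed.

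**A reader might infer that skewness makes the mean-days interval unreliable.** That goes too far. Under the lognormal model with log-SD 0.9 and ratios from 1 to 0.6, the Welch interval covered 92.6% to 95.1%. It disagrees with the rank test mainly because it targets another quantity with less power. Mean days is a legitimate summary of stay and should not be dropped.

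**Strict matching would also catch RRT and ventilator use.** True, but the effect is small. With both rates between 10% and 90% at 80:40, an uncorrected chi-square test and an unpooled normal interval give opposite verdicts for 40 of 65 × 33 = 2,145 count pairs. That is ordinary boundary behaviour and is not part of this point.

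**Conclusion.** The point holds as a moderate-to-minor estimation and reporting defect. The ICU-stay mismatch is explicit in the text; the creatinine mismatch rests on the plain reading of SAP 9.2.1.1. No formal conclusion changes.

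- **Creatinine:** at the planned effect, disagreement is about 2% to 17% of trials and the interval is 0% to 40% wider than needed, for assumed correlations of 0 to -0.7. These figures assume an unadjusted interval for change; an interval for levels was not quantified.
- **ICU stay:** about 2% to 24% with a real effect (assumed lognormal, log-SD 0.6 to 1.0, ratio 0.6 to 0.8, pooled interval), and about 4% to 5% with none.

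Where there is a real effect, the conflict is more often a significant test beside an interval that includes zero. That tendency is strong for creatinine once baseline and change are correlated. For ICU stay it is weaker with a pooled interval than with a Welch interval.

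**What to change.** **SAP 9.2.1.1:** report the ANCOVA-adjusted difference in mean change in creatinine with its model-based 95% interval. Correct the references to levels and to mean days so that both refer to change in creatinine. Arm-level descriptive statistics can stay.

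**SAP 9.2.1.4:** add the Hodges-Lehmann estimate, with the 95% interval obtained by inverting the rank test, as the estimate that accompanies the Wilcoxon p-value. Keep the difference in mean days and its interval, labelled as a supplementary summary.

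**Cost:** a few sentences and standard software output, with no change to sample size, alpha or testing order. The downside is small: ICU stay will carry two intervals, and the Hodges-Lehmann estimate reads as a constant effect in days only under a shift model. The ratio effect assumed in the simulation is not a shift, so the report should say what the estimate means.
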